Because methotrexate depletes folic acid, patients receiving methotrexate may also receive folic acid supplementation under the guidance of the treating gastroenterologist. Reflecting the variability of maintenance options in current clinical care²¹, the recommendation of MTX s.c. as maintenance therapy is intended to help mitigate the confounding effect of different types or lack of immunomodulatory therapy but is not intended to trigger patients being excluded from or leaving the study, e.g. if a treating physician prefers to continue azathioprine, then MTX will not be started concurrently. Details of immunomodulatory therapy will be recorded on a study CRF for concomitant medications.

Participants will complete the following PRO questionnaire at week 0, 12, 24 and 52 study visits:

1. IMPACT (self-report, ages 9-17 years):
<https://miraped.ca/miraresearch/impact/>

If needed, a study timepoint window of +/- 5 days is allowed for all visits/questionnaires/sampling.

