9 STATISTICAL CONSIDERATIONS

9.1 STUDY OUTCOME VARIABLES

The primary outcome evaluation:

The primary efficacy outcome variable is being in sustained remission defined as PCDAI ≤ 10 at 52 weeks from start of therapy AND without steroid dependence and without the need for repeat induction therapy, anti-TNF α , or surgery by 52 weeks from start of therapy.

The secondary outcome evaluations at each study visit include:

- Mean change in PCDAI score from baseline to weeks 4, 12, 24, 36, and 52.
- Mean change in Inflammatory markers: CRP and fecal calprotectin from baseline to weeks 4, 12, 24, 36, and 52.
- Mean change in PRO score (IMPACT questionnaire) from baseline to weeks 4, 12, 24, 36, and 52.
- Improvement (yes vs no) of disease activity (change in PCDAI < 0) rate at weeks 4, 12, 24, 36, and 52.
- Improvement (yes vs no) of C-Reactive Protein (change in CRP < 0 mg/dL) and fecal calprotectin (change in FCP < 0 µg/g) rate at weeks 4, 12, 24, 36, and 52.
- Normalization (yes vs no) of disease activity (PCDAI < 10) rate at weeks 4, 12, 24, 36, and 52.
- Normalization (yes vs no) of C-Reactive Protein (CRP; < 0.5 mg/dL) and fecal calprotectin (FCP; < 250 µg/g) rate at weeks 4, 12, 24, 36, and 52.

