9.4.3 ANALYSIS OF THE SECONDARY OUTCOME VARIABLE(S)

In secondary outcome analyses, the effects of treatment with antibiotics on the microbiome will be assessed to determine whether the signature of group A2 can be modified to move closer to group B.

If this is the case, then groups A2 and B will be pooled and compared against A1. If the microbiome shifts associated with antibiotic use do not make A2 more similar to group B, then groups A1 and B will be pooled and compared against A2 to assess whether there is an additional immune-regulatory effect of azithromycin (in combination with metronidazole) to influence disease flare risk.

Data for secondary outcome variable analysis are independent of the primary outcome variable and will be collected at each study visit.

Continuous secondary outcomes will be summarized at each visit for both the observed values and the changes from baseline. A linear mixed model with timepoint, group, their interaction and baseline as covariates will be used to assess the difference in means between groups at each timepoint. An AR(1) covariance structure will be assumed and the Kenward-Roger degrees of freedom approximation will be utilized. Least squares estimates for the population mean and standard deviation will be provided at each assessment timepoint by group. Missing values will not be imputed. Due to the exploratory nature of the assessments, no correction for multiplicity will be made.

Categorical secondary outcomes variables will be analyzed similarly to the primary outcome (Section 9.4.2).

The analysis of the secondary efficacy parameters will be based on the ITT population.

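### Secondary analyses test group differences at week 4, the visit at which randomization and antibiotics start, and section 9.1 lists IMPACT at two visits where it is not collected

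*Combined protocol and SAP*

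**What the plan says.** Section 9.1 lists the secondary outcomes by visit. PCDAI has three entries. The first is "Mean change in PCDAI score from baseline to weeks 4, 12, 24, 36, and 52". The second is an improvement rate, where any fall in the score counts, reported for the same five visits. The third entry reads "Normalization (yes vs no) of disease activity (PCDAI < 10) rate at weeks 4, 12, 24, 36, and 52". CRP and FCP have the same three kinds of outcome at the same weeks. For quality of life the entry is "Mean change in PRO score (IMPACT questionnaire) from baseline to weeks 4, 12, 24, 36, and 52".

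For continuous outcomes, section 9.4.3 states: "A linear mixed model with timepoint, group, their interaction and baseline as covariates will be used". The purpose given there is a comparison of group means visit by visit. Categorical outcomes follow section 9.4.2, which is Fisher's exact test without covariates. Section 9.4.3 also provides for contrasts with Group B: depending on the microbiome result, "groups A2 and B will be pooled and compared against A1", or A1 and B are pooled against A2.

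Section 9.4.5 takes baseline from Visit 2, which is week 0 in the schedule (section 1.3). Sections 1.1, 1.3 and 4.1 place group assignment and randomization at week 4, with antibiotics from week 4 to week 12. Children with PCDAI above 10 at week 4 are not randomized and go to Group C. On IMPACT, section 4.1 says: "Participants will complete the following PRO questionnaire at week 0, 12, 24 and 52 study visits". The schedule marks the same four visits.

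**The concern.** Week 4 is the starting point of the randomized comparison, yet the plan handles it as a post-baseline efficacy visit. A group difference there cannot be an antibiotic effect if the measurement precedes the first dose. For A1 versus A2 it would be chance. In a contrast pooled with Group B, which is not randomized, it could also be a difference that existed before treatment, and a reader could take it for a drug effect.

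Two of the week-4 tests are also nearly empty by design, because A1, A2 and B contain only children with PCDAI of 10 or less at that visit. Meanwhile the week-4 value, the measurement closest to the start of treatment, is collected but enters the model only as a response.

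The IMPACT entries promise analyses for which no data will exist.

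**Working it through.** **1. Count of comparisons.** Section 9.1 lists four mean changes (PCDAI, CRP, FCP, IMPACT), three improvement rates and three normalization rates: 10 outcomes x 5 weeks = 50. IMPACT listed {4, 12, 24, 36, 52} minus collected after week 0 {12, 24, 52} leaves {4, 36}, two entries without data. So 50 - 2 = 48 have data. At week 4 there are 3 + 3 + 3 = 9, and 9/48 = 19%. Removing them leaves 39.

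**2. PCDAI rates at week 4.** Entry needs PCDAI above 10, or above 7.5 without the height item (section 5.1). A1, A2 and B need 10 or less at week 4. Improvement is therefore met by nearly all, and normalization (below 10) fails only at a score of exactly 10.

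**3. False positives at week 4, A1 versus A2.** Assume 3-6 children per arm and event rates of 0.3-0.7. The true size of Fisher's test at nominal 5% is then 0-2.15%. Three mixed-model tests and four CRP/FCP Fisher tests give 3 x 0.05 + 4 x (0 to 0.0215) = 0.15 to 0.24 expected false positives. The two PCDAI rates add almost none. No figure can be given for the contrasts with Group B, because the documents do not say how A and B differ before treatment.

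**4. Precision at week 12.** Let a, b and c be the correlations of weeks 0-12, 4-12 and 0-4, with unit variances. The documents give no correlations, so r = 0.3-0.9 per 12 weeks is assumed, in three patterns: decay with time, r^(gap/12); the same multiplied by 0.8 for measurement noise; and constant.

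- Reference, week-0 covariate: 1 - a^2. Change from week 0 and observed value give the same residual variance.
- Observed value with week-4 covariate: 1 - b^2.
- Change from week 0 with week-4 covariate only: 2 - 2a - (b - c)^2.
- Observed value with both covariates: 1 - (a^2 + b^2 - 2abc)/(1 - c^2).

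Example, decay, r = 0.5: reference 1 - 0.25 = 0.750. Week-4 covariate 1 - 0.630^2 = 0.603, which is 19.6% lower. Change from week 0 with week 4 only: 1 - (0.630 - 0.794)^2 = 0.973, which is 29.8% higher.

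For PCDAI the week-4 value is cut off at 10. This is modelled as a normal variable truncated above at its 50th, 65th or 80th percentile (remission shares assumed; variance factor k = 0.363, 0.456, 0.583), with each covariance reduced by rho_i4 x rho_j4 x (1 - k). The entry range is not modelled.

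Residual variance at week 12 against the reference, range over r:

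| Outcome, pattern | Observed value, week 4 | Change from week 0, week 4 only | Observed value, both |
|---|---|---|---|
| CRP/FCP, decay | 12.2-31.0% lower | 4.7-48.5% higher | 12.2-31.0% lower |
| CRP/FCP, x0.8 | 7.5-12.3% lower | 16.1-58.0% higher | 7.9-18.5% lower |
| CRP/FCP, constant | 0% | 5.3-53.8% higher | 5.3-22.4% lower |
| PCDAI, decay | 6.6-30.0% lower | 6.2-57.9% higher | 6.6-30.0% lower |
| PCDAI, x0.8 | 0.2-8.4% lower | 21.2-65.2% higher | 3.7-15.0% lower |
| PCDAI, constant | 2.1-8.7% higher | 8.2-59.1% higher | 2.1-20.3% lower |

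Under decay, the gain for CRP and FCP from the week-4 covariate fades to 1.0-13.9% at week 24, 0.1-8.3% at week 36 and 0.0-4.9% at week 52.

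**5. Cost of a second covariate.** The variance factor for q covariates is (N - 3)/(N - q - 3). Section 9.2 gives 25 per arm with 10% drop-out for the larger trial, so N = 50 x 0.9 = 45, and the ratio for q = 2 against q = 1 is 1.050/1.024 = 1.025. With 10 randomized children in the pilot (assumed) it is 1.400/1.167 = 1.20.

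**The case against.** The strongest case against is that little depends on this. Section 9.4.3 calls these assessments exploratory and declares that multiplicity is not corrected. The Netherlands addendum says the sample is too small for efficacy conclusions. The primary Fisher test at week 52 is untouched. All of this stands and keeps the point minor.

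A second objection is that week-0 adjustment is valid. That also stands for A1 versus A2. A reader might infer that adjusting for week 0 biases the randomized comparison. It does not: baseline precedes randomization, and the only possible loss is precision. It is no answer, however, that week 4 is already in the mixed model. There it is a response with its own group effect, so a chance week-4 imbalance is not removed from the week-12 contrast.

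Third, replacing week 0 by week 4 is not always better. For PCDAI, week 4 alone ranges from 9% worse to 8% better in two of the three patterns. If only the covariate is changed while section 9.1 keeps change from week 0 as the response, variance rises in every case computed. This objection stands and shapes the fix.

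Fourth, a reader might take every week-4 value to be pre-dose. The documents support this only for PCDAI, which must be known before allocation. For CRP and FCP the schedule does not fix the order within the visit, and sampling may move by 5 days either way.

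**Conclusion.** The point holds as a minor one. Nine of the 48 secondary comparisons with data are at week 4 and cannot inform on the antibiotic effect, provided that CRP and FCP are sampled before the first dose. Two of the nine are almost fixed by the selection at week 4. IMPACT is listed at two visits without data.

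The possible loss of precision is mainly at week 12. For CRP and FCP it is 0-31% of residual variance, depending wholly on correlations that the documents do not give.

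A reader might also treat the nine tests as independent at exactly 5% and infer a 37% chance of at least one false positive. The plan does not support that figure: the outcomes are correlated, Fisher's test is conservative at these sizes, and two of the rates hardly vary.

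It is worth correcting now because the Netherlands addendum plans to resubmit the protocol for the full-scale trial without substantial change if the pilot proves feasible, and allows pilot data to be included in that trial.

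**What to change.** 1. In sections 9.1 and 9.4.3, test group differences at weeks 12, 24, 36 and 52 only. Report the change from week 0 to week 4 descriptively.
2. In section 9.1, list IMPACT at weeks 12, 24 and 52, with week 0 as covariate.
3. For CRP and FCP, model the observed value, or the change from week 4, with the pre-dose week-4 value as covariate. Do not pair a change-from-week-0 response with a week-4-only covariate, which raises week-12 residual variance by about 5-58% under the assumed correlations.
4. For PCDAI, keep week 0 as the covariate in the pilot.
5. In the full-scale trial, use both week 0 and week 4 for all three outcomes. The week-12 gain is 5-31% for CRP and FCP and 2-30% for PCDAI, before a cost of about 2.5% for the extra covariate with 45 completers. At the bottom of the PCDAI range the two roughly cancel.

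The cost is wording in sections 9.1 and 9.4.3 and a few lines of code. PCDAI, CRP and FCP are already collected at week 4, so no visit or sample is added.

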9.4.4 SAFETY ANALYSES

This study is not evaluating a formal safety outcome variable.

9.4.5 DEMOGRAPHIC AND BASELINE DESCRIPTIVE STATISTICS

Demographic and baseline characteristics will be based on the Intent-to-Treat (ITT) population. For evaluations which are performed at both the screening and baseline visits (Visit 2), baseline values are to be taken from the baseline visit.

Baseline characteristics to be compared between treatments will include age, gender, age at diagnosis, disease location and behavior (classified using the Paris classification scheme), disease activity (PCDAI score), CRP values, FCP values, and anthropometrics including height and weight z-score.

9.4.6 PLANNED INTERIM ANALYSES

Not applicable

9.4.7 SUB-GROUP ANALYSES

A priori subgroup analyses are unlikely to be powered sufficiently in this pilot trial. We will assess the effect of different gender and clinical phenotype (e.g. isolated colonic Crohn's vs isolated ileal Crohn's vs

ileo-colonic involvement of the lower GI tract) although these are often influenced by disease severity at diagnosis and their effects may be confounded with the effects of the disease severity. All results will be considered exploratory.

9.4.8 TABULATION OF INDIVIDUAL PARTICIPANT DATA

Participant data will be recorded individually by measure and for each time point.

9.4.9 EXPLORATORY ANALYSES

Exploratory analyses will involve the microbiome sequence data obtained from stool samples collected during the study. Changes in microbiome taxonomic composition and genome (metagenome) composition will be compared to changes in disease activity measured at each study visit, while taking into account other clinical phenotypic data.

10 SUPPORTING DOCUMENTATION AND OPERATIONAL CONSIDERATIONS

10.1 REGULATORY, ETHICAL, AND STUDY OVERSIGHT CONSIDERATIONS

10.1.1 INFORMED CONSENT PROCESS

10.1.1.1 CONSENT/ASSENT AND OTHER INFORMATIONAL DOCUMENTS PROVIDED TO PARTICIPANTS

Consent forms describing in detail the study intervention, study procedures, and risks are given to the participant and written documentation of informed consent is required prior to starting intervention/administering study intervention. The following consent materials are submitted with this protocol:

Information and Authorization Form

Information and Consent Form

Assent Form

10.1.1.2 CONSENT PROCEDURES AND DOCUMENTATION

Informed consent is a process that is initiated prior to the individual's agreeing to participate in the study and continues throughout the individual's study participation. Consent forms will be Institutional Review Board (IRB)-approved and the participant will be asked to read and review the document. The investigator will explain the research study to the participant and answer any questions that may arise. A verbal explanation will be provided in terms suited to the participant's comprehension of the purposes, procedures, and potential risks of the study and of their rights as research participants. Participants will have the opportunity to carefully review the written consent form and ask questions prior to signing. The participants should have the opportunity to discuss the study with their family or surrogates or think about it prior to agreeing to participate. The participant will sign the informed consent document prior to any procedures being done specifically for the study. Participants must be informed that participation is voluntary and that they may withdraw from the study at any time, without

prejudice. A copy of the informed consent document will be given to the participants for their records. The informed consent process will be conducted and documented in the source document (including the date), and the form signed, before the participant undergoes any study-specific procedures. The rights and welfare of the participants will be protected by emphasizing to them that the quality of their medical care will not be adversely affected if they decline to participate in this study.

10.1.2 STUDY DISCONTINUATION AND CLOSURE

This study may be temporarily suspended or prematurely terminated if there is sufficient reasonable cause. Written notification, documenting the reason for study suspension or termination, will be provided by the suspending or terminating party to study participants, investigator, funding agency, the Investigational New Drug (IND) sponsor and regulatory authorities. If the study is prematurely terminated or suspended, the Principal Investigator (PI) will promptly inform study participants, the Institutional Review Board (IRB), and sponsor and will provide the reason(s) for the termination or suspension. Study participants will be contacted, as applicable, and be informed of changes to study visit schedule.

Circumstances that may warrant termination or suspension include, but are not limited to:

- Determination of unexpected, significant, or unacceptable risk to participants
- Demonstration of efficacy that would warrant stopping
- Insufficient compliance to protocol requirements
- Data that are not sufficiently complete and/or evaluable
- Determination that the primary outcome variable has been met
- Determination of futility

The study may resume once concerns about safety, protocol compliance, and data quality are addressed, and satisfy the sponsor, IRB and/or FDA/Health Canada.

10.1.3 CONFIDENTIALITY AND PRIVACY

Participant confidentiality and privacy is strictly held in trust by the participating investigators, their staff, and the sponsor(s) and their interventions. This confidentiality is extended to cover testing of biological samples and genetic tests in addition to the clinical information relating to participants. Therefore, the study protocol, documentation, data, and all other information generated will be held in strict confidence. No information concerning the study or the data will be released to any unauthorized third party without prior written approval of the sponsor.

All research activities will be conducted in as private a setting as possible.

The study monitor, other authorized representatives of the sponsor, representatives of the Institutional Review Board (IRB), regulatory agencies or pharmaceutical company supplying study product may inspect all documents and records required to be maintained by the investigator, including but not limited to, medical records (office, clinic, or hospital) and pharmacy records for the participants in this study. The clinical study site will permit access to such records.

The study participant's contact information will be securely stored at each clinical site for internal use during the study. At the end of the study, all records will continue to be kept in a secure location for as long a period as dictated by the reviewing IRB, Institutional policies, or sponsor requirements.

Study participant research data, which is for purposes of statistical analysis and scientific reporting, will be transmitted to and stored at the Amsterdam UMC, location AMC (Amsterdam, The Netherlands). This will not include the participant's contact or identifying information. Rather, individual participants and their research data will be identified by a unique study identification number. The study data entry and study management systems used by clinical sites and by the Amsterdam UMC research staff will be secured and password protected. At the end of the study, all study databases will be de-identified and archived at the Amsterdam UMC, location AMC.

To further protect the privacy of study participants, a Certificate of Confidentiality will be issued by the National Institutes of Health (NIH). This certificate protects identifiable research information from forced disclosure. It allows the investigator and others who have access to research records to refuse to disclose identifying information on research participation in any civil, criminal, administrative, legislative, or other proceeding, whether at the federal, state, or local level. By protecting researchers and institutions from being compelled to disclose information that would identify research participants, Certificates of Confidentiality help achieve the research objectives and promote participation in studies by helping assure confidentiality and privacy to participants.

10.1.4 FUTURE USE OF STORED SPECIMENS AND DATA

Data collected for this study will be analyzed and stored at the Amsterdam UMC, location AMC. After the study is completed, the de-identified, archived data will be transmitted to and stored at the Amsterdam UMC, location AMC for use by other researchers including those outside of the study. Permission to transmit data to the Amsterdam UMC will be included in the informed consent.

With the participant's approval and as approved by local Institutional Review Boards (IRBs), de-identified biological samples will be stored at the Amsterdam UMC with the same goal as the sharing of data with the Amsterdam UMC. These samples could be used to research the causes of inflammatory bowel diseases (IBD), its complications and other conditions for which individuals with IBD are at increased risk, and to improve treatment. The Amsterdam UMC will also be provided with a code-link that will allow linking the biological specimens with the phenotypic data from each participant, maintaining the blinding of the identity of the participant.

During the conduct of the study, an individual participant can choose to withdraw consent to have biological specimens stored for future research. However, withdrawal of consent with regard to biospecimen storage may not be possible after the study is completed.

When the study is completed, access to study data and/or samples will be provided through the Amsterdam UMC, location AMC.

10.1.6 SAFETY OVERSIGHT

Safety oversight will be under the direction of a Data and Safety Monitoring Board (DSMB) composed of individuals with the appropriate expertise, including experts in clinical care and trials in pediatric gastroenterology and inflammatory bowel disease. Members of the DSMB should be independent from the study conduct and free of conflict of interest, or measures should be in place to minimize perceived conflict of interest. The DSMB will meet at least semiannually to assess safety and efficacy data on each arm of the study. The DSMB will operate under the rules of an approved charter that will be written and reviewed at the organizational meeting of the DSMB. At this time, each data element that the DSMB needs to assess will be clearly defined. The DSMB will provide its input to the study sponsor [name] [name] as well to [name].

